1.0 LIST OF ABBREVIATIONS

Abbreviation	Definition
AE	Adverse Event
AIDS	Acquired Immune Deficiency Syndrome
ASI-Lite	Addiction Severity Index-Lite
CAP	College of American Pathologists
CJ-DATS	Criminal Justice Drug Abuse Treatment Studies
CLIA	Clinical Laboratory Improvement Amendment of 1988
CNS	Central Nervous System
COWS	Clinical Opiate Withdrawal Scale
CRF	Case Report Form
DATCAP	Drug Abuse Treatment Cost Analysis Program
DE	Drug Education
DEA	Drug Enforcement Agency
DL	Dose Logs
DMC	Data Management Center
DSMB	Data and Safety Monitoring Board
DSM-IV	Diagnostic and Statistical Manual of Mental Disorders Fourth Edition
DSM-5	Diagnostic and Statistical Manual of Mental Disorders Fifth Edition
eCRF	Electronic Case Report Form
FCG	Electrocardiogram
FDA	Food and Drug Administration
GCP	Good Clinical Practice
HCV	Henatitis C. Virus
HIV	Human Immunodeficiency Virus
ICH	International Conference on Harmonisation
IRB	Institutional Review Board
IND	Investigational New Drug
LFT	Liver Function Test
Ma	Milligrams
NDA	New Drug Application
NTX	Naltrexone
NIDA	National Institute on Drug Abuse
NIH	National Institutes of Health
PN	Patient Navigator
PNV	Patient Navigator and Vivitrol Condition
PI	Principal Investigator
RAB	Risk Assessment Battery
SAE	Serious Adverse Event
SOWS	Subjective Opiate Withdrawal Scale
SSI-M	Modified Scale for Suicide Ideation
UDS	Urine Drug Screen
TEA	Treatment Effects Assessment
TES	Treatment Effectiveness Score
TLFB	Time Line Follow Back
VAS	Visual Analog Scale
VI	Extended-Release Naltrexone (as Vivitrol®)

2.0 ABSTRACT

2.1 Study Objective

The aim of this trial is to assess the clinical utility, effectiveness, and cost implications of treatment for incarcerated offenders with opioid use disorders who are randomly assigned to one of three treatment conditions to include a depot formulation of naltrexone (Vivitrol®) only (VI), a patient navigation (PN) procedure plus Vivitrol (PNV), and a drug education procedure (DE) before being released to the community. This trial will investigate whether effective medication therapy used in non-incarcerated populations will also be effective in incarcerated individuals. Empirical evidence demonstrates that starting treatment before release greatly increases the probability of successful outcome including reduced alcohol and drug use, increased employment rates, and reduced recidivism rates.

2.2 Study Design

This four-year randomized, open-label trial will examine the feasibility, efficacy, and net economic benefits of VI for opioid addiction delivered with and without a platform of PN provided for six months compared against a DE condition. Before release from jail, participants in the VI and PNV conditions will receive their first Vivitrol injection (and those in the PNV condition will meet with a Patient Navigator) and will then be scheduled for medication management sessions twice monthly for months 1-3, with monthly injections in months 4-6. Participants in the PNV condition will meet with a PN who will provide behavioral assistance to overcome possible barriers to community outpatient treatment and will be provided with a schedule of possible community treatment programs. Participants in the DE condition will receive education designed to reduce the likelihood of overdose on the same schedule as the VI and PNV groups. All participants will receive weekly study phone calls to assess well being and possible adverse events.

2.3 Study Participants

Participants will be 150 individuals, who meet DSM-5 criteria for opioid use disorders, are 18 years and older, who have been detoxified from opioids in the Metropolitan Detention Center in Albuquerque, New Mexico. This study will include only those participants for whom the study physician determines that possible treatment with the study drug is in the best interest, and informed consent will be obtained.

2.4 Interventions

All participants will be scheduled for twice-monthly medical management and assessment appointments for the first three months of the 24-week post-release intervention phase, with monthly appointments for months 4-6. Eligible participants will be randomly assigned to treatment condition (VI, PNV, DE) in equal numbers. VI and PNV participants will undergo a naloxone challenge to ensure opioid abstinence at the time of Vivitrol induction. Those in the PNV condition will be provided with a PN who will facilitate attendance at outpatient treatment programs as well as assist with other needs. The DE group will not receive any medication but will be scheduled for assessments and education on drugs of abuse, maintaining abstinence, and methods for avoiding overdoses on the same schedule as the other two groups. The DE group will also be

provided with naloxone kits to be used in the event of overdose. All groups will also be provided with referrals to community-based substance abuse treatment programs.

2.3 Assessments

Screening/baseline assessments will include a medical and psychiatric history, physical examination, clinical lab tests (blood chemistry, hematology, urinalysis and hepatitis screening), 12-lead electrocardiograph, vital signs, pregnancy test (for females), and urine toxicology screen. Assessments completed at months 1, 3, 6, 7, and 12 include drug use, dosing and protocol compliance, pregnancy tests for females of child-bearing potential, and other measures of status and functioning. Safety of study participants and intervention tolerability will be assessed throughout the study by collection of adverse events, suicidality, and measures of drug use. Participants who experience an adverse event deemed as compromising their safety will be discontinued from participation and provided referrals for medical care.

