5.2 Duration of Study and Clinic Visit Schedule

The duration of this study will include a projected 2-4 weeks for screening/baseline assessments and medication induction, and a 24-week intervention phase to include, specific to assigned condition, medication, PN, DE, assessments, and medical management. The screening phase will differ in the length of time needed to complete eligibility assessments, random assignment, and to complete medication induction in the VI and PNV conditions. Induction will be scheduled to occur within 4 weeks of discharge. Screening assessments will include the collection of laboratory samples and medical assessments to ensure participant safety. Confirmation of opioid-free status (UDS and naloxone challenge) before medication induction will take approximately two hours. Assessment visits at 1, 3, 6, 7, and 12-months will take about 30-60 minutes depending on the scheduled assessments. Medical management visits will last from 20–60 minutes and will include collection of UDS and other short measures of status and well-being. PN sessions are expected to take about 60 minutes. DE sessions will take about 20 minutes.

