7.15 Participant Reimbursement

Study participants will receive gift cards or cash as compensation for time, travel, parking, and other costs borne by the participant. Participants will be provided with medical management at no cost, and those in the VI and PNV conditions will receive no-cost medication.

Incentives will be provided for participating in screening, twice-monthly medical management visits in months 1-3 and monthly visits in months 4-6 during the intervention phase, and assessment visits at months 1, 3, 6, and 12. A \$25 incentive will be provided for screening; \$20 for each of 9 medical management visits (\$180), \$40 for each of 3 post-release assessment visits (\$120), and \$80 for a final visit at month 12. Each participant will be eligible to receive \$405.

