8.0 STUDY ASSESSMENTS

Measures and instruments will be used to ensure a comprehensive assessment of status and functioning variables. These data, along with the DATCAP, will also be used to support the economic analysis. (The DATCAP will be administered during Year 2.) On average, screening and eligibility assessments will be completed in 4-6 hours (specific to treatment group). Post-release assessments will be completed in approximately 30-60 minutes. Medication Management visits are expected to take approximately 30-60 minutes.

Timepoints	Screening	Pre-	Post-release	
_		release		
Clinic Visits			Medical Mgmt	Assessments
				Months 1, 3,
				6, 7, 12
Measures				
Safety & Med. Measures				
Physical Exam / Med History	Х			
Injection site inspection	Х		X	
Vitals	Х		X	
12-lead ECG	Х			
Clinical Lab Tests	Х			
HIV Test	Х			
Pregnancy Test	Х		X	
Prior/Concomitant Meds	Х		X	
AEs			X	Х
Drug Use Measures				
DSM-5 Checklist	Х			
COWS (Withdrawal)	Х			
SOWS (Withdrawal)	Х			
Urine Drug Screen (UDS)	Х	Х	X	Х
Substance Use Report (TLFB)	Х	Х	X	Х
VAS (Craving)	Х	X	X	X
Crime and Recidivism				
Self-Report Arrest/Tx History			X	Х
Arrest Records				Х
CJ-DATS Crime Grid	Х			
HIV Risk Measure				
HIV-GAIN	Х			X
Cost				
Form 90				

Table	1. Data	Collection	Time and	Event	Schedule
I UDIC	I. Dutu	00110011011	This and		ouncaute

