8.1.7 Pregnancy and Birth Control Assessment

Pregnancy test information will be collected for female participants and include test results, and self-reports of birth control method(s).

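### Section 2.3 and Table 1 list different post-release pregnancy tests, and nothing in the documents asks for a repeat test before the first Vivitrol injection (minor, safety only)

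*Combined protocol and SAP*

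**What the plan says.** **Post-release tests.** The abstract, Section 2.3 (Assessments), states: "Assessments completed at months 1, 3, 6, 7, and 12 include drug use, dosing and protocol compliance, pregnancy tests for females of child-bearing potential". The same section lists a pregnancy test for women at screening.

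In Table 1 (Section 8.0), the "Pregnancy Test" row is marked under Screening and under post-release Medical Mgmt. It is blank under Pre-release and under Assessments (months 1, 3, 6, 7, 12). Section 8.1.7 says what pregnancy information is recorded but names no visit.

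Section 2.4 (Interventions) describes "twice-monthly medical management and assessment appointments for the first three months", then monthly appointments in months 4-6. Section 7.15 pays "for each of 9 medical management visits".

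**Induction.** Section 2.2: "Before release from jail, participants in the VI and PNV conditions will receive their first Vivitrol injection". Section 5.2: "The duration of this study will include a projected 2-4 weeks for screening/baseline assessments and medication induction", and "The screening phase will differ in the length of time needed to complete eligibility assessments, random assignment, and to complete medication induction" in the two medication arms.

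Section 7.4.1 sets four steps before the first injection: self-reported abstinence, an opioid-negative urine screen shortly before the challenge, completion of the screening and eligibility assessments, and a naloxone challenge. Opioid status is therefore rechecked close to the injection. Pregnancy is not mentioned.

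Pregnancy is an exclusion (Section 5.3.2) and ends study medication if it occurs (Section 7.13, Appendix A).

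**The concern.** Site staff working from Table 1 and staff working from the abstract would test on different days, and Section 8.1.7, where one would look for the answer, does not choose between them. Table 1 followed alone omits months 7 and 12. Section 2.3 followed alone omits the medical management visits that fall outside assessment months, when injections are still being given.

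The induction question is separate. The first injection is given in jail, and Section 7.5.1 says that naltrexone stays detectable for at least 30 days, so a dose cannot be withdrawn once given. The protocol rechecks one condition for safe dosing (freedom from opioids) just before injection, but relies on the screening result for another (not being pregnant). At stake is avoidable exposure in a small number of women, and consistent detection of pregnancies that the protocol wants followed to outcome.

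**Working it through.** The plan has no figure to reproduce. The check sets the texts side by side and counts visits.

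**1. Is Table 1 read correctly?** The pregnancy row has the same pattern as Vitals and Prior/Concomitant Meds: Screening and Medical Mgmt only. The AE and urine drug screen rows carry marks in both post-release columns, so the columns are distinguishable. The text of Section 8.1.8 places vital signs at screening and medical management visits, which agrees with that reading.

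**2. The two schedules.**

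| Time | Section 2.3 (Assessments) | Table 1 |
|---|---|---|
| Screening | test | test |
| Pre-release | not mentioned | blank |
| Months 1, 3, 6 | test | test, if held with a medical management visit |
| Other medical management visits | not mentioned | test |
| Months 7, 12 | test | blank |

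**3. Post-release counts per woman.**
- Table 1: 2 × 3 + 1 × 3 = 9 medical management visits, matching Section 7.15.
- Section 2.3: 5 visits.
- Overlap: at most 3 (months 1, 3 and 6), because Section 2.4 combines medical management and assessment appointments.
- Only in Table 1: 9 − 3 = 6 at full overlap.
- Only in Section 2.3: 5 − 3 = 2 (months 7 and 12).
- Both lists followed together: 9 + 5 − 3 = 11.

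**4. Order of events before the first injection.**
- Section 7.2: randomization follows receipt of all results and confirmation of eligibility.
- Section 7.4.1, Step 3: screening and eligibility assessments must be complete before induction.
- Hence a screening pregnancy test precedes the injection.
- Section 5.2: screening and induction together take a projected 2-4 weeks, so the result could be up to about 4 weeks old.
- Section 7.4.1, Step 4: a positive naloxone challenge delays induction further. No maximum age for the pregnancy result is stated.
- Section 5.3.1: only 48 hours' detention is required. A conception shortly before detention could be too recent to show at screening. This assumes that a test can miss a very early pregnancy; the documents give no test sensitivity.

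**5. How many first injections?** VI and PNV together: 150 × 2/3 = 100 participants. Section 5.5 gives 87% male in the jail, hence 13% female. The trial's own female share is not stated, so a range is assumed:
- 10%: 100 × 0.10 = 10
- 13%: 100 × 0.13 = 13
- 25%: 100 × 0.25 = 25

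These are upper counts, treating every woman as of child-bearing potential. They count injections, not exposed pregnancies.

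**The case against.** Much of the case on the other side stands.

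- A reader might infer that the first injection can be given with no pregnancy test at all. The documents do not support that. Section 7.2 and Step 3 of Section 7.4.1 make completed screening a condition. Only the age of the result is open.
- A reader might infer a risk of conception throughout the 2-4 weeks. But recruitment, screening and the first injection all take place in jail, so the realistic case is an early pregnancy already present and missed at screening. The contraception rule in Section 5.3.2 lowers the risk further.
- The two schedules need not exclude each other. Section 2.3 is an abstract and lists what assessments include, not the only times for testing. A site could follow both. Table 1 is also the denser schedule while injections are being given. What remains is that neither source gives the full list.
- It is tempting to state how many weeks of late naltrexone exposure the month 6 test would leave uncovered. That depends on how early a test detects pregnancy, which the documents do not give, so no such figure is offered.
- Section 7.5.1 defers to the package insert and Section 12.1 to an Operations Manual. Neither is available, and either may call for a test at induction. The statement is therefore limited to these documents.
- Section 7.13 and Appendix A follow known pregnancies to outcome whether or not a scheduled test found them.

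The induction gap is not a contradiction between texts: both sources agree on a screening test and neither asks for another. It is a suggested addition.

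**Conclusion.** The point holds as a minor safety and scheduling matter. Section 2.3 and Table 1 disagree on months 7 and 12 and on at least 6 of 9 medical management visits, and Section 8.1.7 does not settle it. A screening test precedes the first injection, but nothing in these documents requires a repeat, so an early pregnancy missed at screening would not be rechecked before a month-long dose.

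The scale is at most 10 to 25 first injections. It rests on assumed female shares of 10-25% and on the assumption that a screening test can miss a very early pregnancy. No number of exposed pregnancies can be derived. There is no effect on sample size, power, alpha or the primary analysis.

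**What to change.** 1. **Section 7.4.1, Step 2.** Add: *Women of child-bearing potential must also have a negative urine pregnancy test on this sample before the naloxone challenge and first injection.* With the one day of oral naltrexone that follows the challenge, the result would be about a day old at injection.
2. **Table 1, pregnancy row.** Keep the Screening and Medical Mgmt marks. Add a Pre-release mark footnoted *VI and PNV, before first injection*. Add an Assessments mark footnoted *months 7 and 12; months 1, 3 and 6 are covered by the medical management visit*.
3. **Section 2.3 (Assessments).** Keep the month list and add *and at induction (VI and PNV) and medical management visits*.

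Both sources then give the same list: screening, induction in the medication arms, and the 11 post-release tests counted above.

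**Cost.** Wording in two sections and two footnoted table marks. About 10-25 extra urine tests at induction, on a sample already collected, plus a repeat for anyone whose challenge is repeated. Months 7 and 12 add nothing to what Section 2.3 already lists. A site that has been following Table 1 would add two tests per woman, at visits where Table 1 already marks a urine drug screen. Section 7.15 pays for assessments at months 1, 3, 6 and 12 but does not list month 7, so the sponsor should confirm that visit when making the change.

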2.4 Analyses

The primary outcomes include opioid use and DSM-5 diagnosis of opioid use disorder via modified CIDI-2 Substance Abuse Module at 6-months post-intervention. Opioid use will be computed from the Timeline Follow-Back (TLFB) as the number of days of self-reported opioid use in the past 30 days at the 6-month assessment. The cost analysis will measure and value resources associated with VI, including medical personnel (physician/nurses), labs, and medications. To ascertain cost-effectiveness ratios of VI and PNV, cost data will be compared to changes in key clinical measures of effectiveness.

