7.8 Medical Management

At each clinic visit, participants will meet with study physicians and other study personnel such as nurses, research assistants, and counselors, to review urine results, discuss adverse events, consider the study medication effects and side effects, and discuss other pertinent issues in keeping with sound medical practice. Participants' engagement in self-help groups such as 12-step is permitted. Medical Management visits will occur twice-monthly during months 1-3, and monthly during months 4-6, and Vivitrol injections will be provided monthly to participants in the VI and PNV conditions.

7.9 "Rescue" Protocol

Participants who develop significant problems, who cannot tolerate naltrexone, or whose preexisting condition worsens during the study may receive increased levels of care deemed necessary by the Study Physician, and they will be referred to other treatment resources.

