8.2 Drug Use Measures and Psychological Measures

8.2.1 Substance Use Report: Timeline Follow-Back (TLFB)

The TLFB will be used to elicit participants' self-reported use of alcohol and illicit substances. At screening, substance use reported by the participant for the prior 30-day period will be assessed. The TLFB will be administered at each study visit throughout the medication phase, at the post-medication visit, and at follow-up to document the participant's self-reported use of substances for each day since the previous assessment.

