10.0 STATISTICAL ANALYSES

The project emphasizes evaluation of the clinical utility of Vivitrol in jail inmates as compared with a Drug Education condition (DE), while descriptive statistics will provide an overall assessment of the implementation of the protocol.

Analyses will include an Intent-to-treat (ITT) design such that all randomized participants who received at least one dose of medication (VI, PNV), or received at least one session of drug education (DE) will be included who did not violate the protocol in a way that could potentially affect the efficacy results. Participants will be excluded from the Protocol Population (PP) if:

- 1. concomitant medication that is known to have significant clinical effect on primary or secondary endpoints was administered.
- 2. Violations of the inclusion or exclusion criteria are judged to affect the efficacy evaluations.

Subjects in the PP population will be allocated to treatment groups in the analysis based on the actual treatment they received. If there is substantial difference between the ITT population and the PP population, all analyses described below will be performed using only subjects in this group.

All statistical tests will be performed using two-sided .05 significance levels, unless otherwise stated. All comparisons between treatments will be reported with parameter estimates and 95% confidence intervals. For parameters measured at baseline and subsequently, the variables of interest are changes from baseline.

Post-baseline variables will not be imputed; estimates can be obtained using the hierarchical models specified below under the assumption of missing at random. For the primary outcome measure, diagnosis at six months, subjects who have dropped out for whatever reason will be considered to retain the diagnosis. Other outcome measures for which data are missing will be imputed using multiple imputation methods. Sensitivity analyses will repeat specific analyses using permutation tests of at least 1000 samples.

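### The primary opioid-days count runs back from the date of the 6-month visit, with no visit window and no rule for a late or missed visit, although the daily TLFB could supply a fixed 30-day window

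*Combined protocol and SAP*

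**What the plan says.** **Definition.** The Abstract (2.4 Analyses) takes opioid use from the TLFB as "the number of days of self-reported opioid use in the past 30 days at the 6-month assessment". Sections 6.1 and 10.1 name opioid use as a primary outcome but do not define it.

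**Data collection.** Section 8.2.1: "The TLFB will be administered at each study visit throughout the medication phase, at the post-medication visit, and at follow-up", in order "to document the participant's self-reported use of substances for each day since the previous assessment". Section 5.2: "Assessment visits at 1, 3, 6, 7, and 12-months will take about 30-60 minutes"; Table 1 places these after release. Section 7.8: "Medical Management visits will occur twice-monthly during months 1-3, and monthly during months 4-6".

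**Missing values.** Section 10.0 says "Post-baseline variables will not be imputed", relying on hierarchical models under missing at random. It then keeps the diagnosis for dropouts and adds: "Other outcome measures for which data are missing will be imputed using multiple imputation methods". Section 10.4 separates intermittent gaps in active participants from dropout. Section 10.4.1 allows dropping cases, substituting means or estimating. Section 7.3 counts those who leave after induction or the first DE session as failures.

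**Time origin.** Section 6.1 counts six months from randomization. Item 3 in section 6.2 places the six-month assessment after release, at the end of the intervention phase. The Abstract (2.4 Analyses) places the primary outcomes six months after the intervention.

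**The concern.** The definition ties a primary outcome to a visit date, while the instrument behind it is a running daily calendar. Two consequences follow from the text.

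- **Late visits.** Participants are measured over different calendar periods, and the plan sets no limit on how different. After a late month-6 visit, the form holds the intended days as well as the later ones, but the definition counts the later ones.
- **Missed visits.** A participant who misses month 6 and attends later reports every day since the last visit, including the target days. The definition gives no value, and no section tells the analyst to use the later form.

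The plan gives reason to expect attendance to differ by arm. Section 10.3 expects less dropout in VI than in DE, and section 7.6.2 describes navigators as helping patients keep appointments. The trial is open label (7.14). A window that depends on attendance could thus depend on arm. Relying on a model or on imputation where days were actually reported is also avoidable.

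**Working it through.** **1. The plan's own figure.** Section 10.3 expects about 120 evaluable participants from 150 (50 per arm) at 10–20% dropout.
- 150 × (1 − 0.20) = 120, which matches, with 30 lost.
- 150 × (1 − 0.10) = 135, with 15 lost.

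**2. Late visit.** For a visit d days late, days replaced = min(30, d) and overlap = max(0, 30 − d)/30. The documents state no limit on d.

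| Days late | Intended days replaced | Overlap |
|---|---|---|
| 7 | 7 | 23/30 = 77% |
| 14 | 14 | 16/30 = 53% |
| 21 | 21 | 9/30 = 30% |
| 30 | 30 | 0% |

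The count changes by d × (p1 − p0), where p0 and p1 are the shares of days with use before and after the target date. If the rate is constant, the expected change is zero. With assumed values p0 = 0.20 and p1 = 0.40, a 14-day delay gives 16 × 0.20 + 14 × 0.40 = 8.8 days instead of 30 × 0.20 = 6.0. These rates are illustrative and do not come from the documents.

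**3. Which forms hold the target days.**
- Month 6 attended late: the month-6 form reaches back to the previous visit, about month 5, so with the earlier form it covers the window.
- Month 6 missed, month 7 attended: the month-7 form covers the window, with recall of about 1–2 months.
- Months 6 and 7 missed, month 12 attended: the window is covered, but at about 6–7 months' recall.
- Never seen again: the month-5 form stops about where the window begins, so almost nothing is recorded.

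**4. Missed visit: what can be recovered.** The share of participants who miss month 6 and return is not in the documents. I take 0–50% as an assumption and let the 15–30 lost stand for missing six-month values.
- Recovered: 0 to 0.5 × 15 = 7.5 at 10% dropout, and 0 to 0.5 × 30 = 15 at 20%. The range overall is 0–15.
- Per arm at 20%: 40 rises to at most 40 + 0.5 × 10 = 45.
- Power of a two-sample t-test, two-sided 0.05, d = 0.5: 0.598 at 40 per arm and 0.650 at 45.
- At 10% dropout: 45 rises to at most 47.5 per arm, and power from 0.650 to 0.674.

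Section 10.3 states 0.80 power at an effect of 0.5. A comparison of 40 with 40 does not give that. It is a separate matter and does not affect this point.

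**5. Anchor.** Section 5.2 puts induction within 4 weeks of discharge. If randomization is close to induction, the randomization and release anchors differ by 0–28 days, leaving as few as 30 − 28 = 2 days common to the two windows. The gap may be larger if randomization is earlier.

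**The case against.** The strongest reply is that the plan is silent here, not wrong. The definition sits in an abstract, and nothing says that later TLFB forms are to be discarded. A sensible analyst could assemble the window across forms. That is fair as far as intent goes. But this is the only definition given for a primary outcome, and followed literally it moves the window and leaves reported days unused.

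A reader might infer more, and the documents do not support it:
- **That missed visits will be imputed.** Section 10.0 both rules out imputation of post-baseline variables and prescribes multiple imputation for other outcomes, and sections 7.3, 10.4 and 10.4.1 add further rules. The handling is undetermined.
- **That the TLFB already holds everyone's days.** It does so only for late attenders and those who return.
- **That the treatment contrast is biased by a known amount.** Comparing attenders with everyone would test a complete-case analysis. The plan's models or imputation could draw on earlier TLFB visits.
- **That a month-6 form covering fewer than 30 days is an error.** Joining forms is what a day-by-day record is for.

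Two further objections stand. Section 7.15 lists no payment for month 7 but $80 for month 12, so month-7 returns may be few. Recalling single days after 6–7 months is weak; if DE misses more visits, such values would gather in DE. Using them is a trade-off. The gain in power is also small, in a study that section 10.3 describes as preliminary.

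**Conclusion.** The concern holds in this form. The primary opioid-use count has no fixed window, no visit window and no rule for late or missed visits, while the trial already collects the daily record needed to supply them.

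The late-visit effect is arithmetic and needs no assumption about return: d of 30 intended days are replaced at d days late. How many visits will be late, and whether use differs between the two periods, is unknown. The missed-visit gain rests on an assumed 0–50% return: 0–15 outcomes, and power at d = 0.5 of at most about 0.65 against about 0.60 in the 20% case. It could be nil. No size of bias in the treatment comparison can be stated from the documents.

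The case for acting is that the fix is cheap, concerns a primary outcome, and can credibly be settled only before the data are analysed.

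**What to change.** In the Abstract (2.4 Analyses) and sections 6.1 and 10.1:

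1. Choose one time origin among randomization, release and end of intervention, and use it throughout.
2. Define opioid use as TLFB days of use in the 30 calendar days ending on the month-6 date from that origin.
3. Assemble the count from all TLFB forms covering those days, including a late month-6 form and the month-7 form.
4. Apply the missing-data rule only to days that no such form covers, and reconcile sections 7.3, 10.0, 10.4 and 10.4.1 into one rule. Participants who never return depend on it.
5. Use month-12 recall only in a sensitivity analysis.

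Items 3 and 5 suit a target date near the month-6 visit. If six months after the end of intervention is truly meant, the date falls close to the month-12 visit and the source forms must be named afresh.

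The cost is wording and some programming, with no new visits or data, and recall of about 1–2 months for values filled from month 7.
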